3.5.4.2 Additional analyses of key safety laboratory data

The following analyses of key safety laboratory data will be summarized for on-treatment period and on-study period respectively.

The number and percent of patients falling in each of the following categories will be tabulated:

- The higher of $\text{ALT} > 3 \times \text{upper limit of normal (ULN)}$ or $\text{ALT} > 2 \times \text{Safety Baseline}$
- $\text{ALT/AST} > 3 \times \text{ULN}$
- $\text{ALT/AST} > 5 \times \text{ULN}$
- $\text{ALT/AST} > 8 \times \text{ULN}$
- $\text{ALT/AST} > 10 \times \text{ULN}$
- $\text{ALT/AST} > 20 \times \text{ULN}$
- $\text{ALT} > 3 \times \text{ULN} - \leq 5 \times \text{ULN}$
- $\text{ALT} > 5 \times \text{ULN} - \leq 10 \times \text{ULN}$

- ALT > 10 x ULN - ≤ 20 x ULN
- Total bilirubin > 2 x ULN, and
- ALP > 2 x ULN and (safety baseline ALP < 2 x ULN or safety baseline ALP missing) .

The number and percent of patients falling in each of the following categories based on confirmed results after first dose will be tabulated (A confirmed value is based on a consecutive lab value within 7 days. If that value is in the same or worse category the initial value is confirmed. If the consecutive value is in a better category then the initial value is confirmed using the consecutive value category. If there is no retest within 7 days then the initial value is presumed confirmed. If there are multiple results on the same day, then the worst value will be utilized in the analysis):

- The higher of ALT/AST > 3 x ULN or ALT/AST > 2 x Baseline, which is confirmed
- ALT/AST > 3 x ULN, which is confirmed
- ALT/AST > 5 x ULN, which is confirmed
- ALT/AST > 10 x ULN, which is confirmed
- ALT/AST > 20 x ULN, which is confirmed

For patients having at least 3-fold or greater elevations above the ULN for ALT or AST, a listing of all of the ALT, AST, total bilirubin, INR, and alkaline phosphatase records will be provided. Other liver abnormalities including elevation of ALT (>3 x ULN) accompanied by elevated total bilirubin (> 2 x ULN), elevation of ALT (> 3 x ULN) accompanied by INR > 1.5 x ULN, elevation of ALT (> 3 x ULN) accompanied by elevated total bilirubin > 2 x ULN and ALP < 2 x ULN, and elevation of ALT/AST in temporal association with nausea, vomiting, anorexia, abdominal pain, or fatigue will be reviewed by the study team and summarized if needed.

The following hematology and hepatic enzymes lab results will be categorized by value range based on Guidance for Industry – Toxicity Grading Scale for Healthy Adult and Adolescent Volunteers Enrolled in Preventive Vaccine Clinical Trials (September 2007), and the incidence of shift from safety baseline to worst post-baseline value taken after the first dose during on-treatment period will be summarized. If a patient is missing a safety baseline value but has a post-baseline value, then the baseline assessment will be labeled as “unknown”. Likewise, if a patient has a baseline value but has no post-baseline values, then the worst value will be labeled as “unknown”. Number and proportion of patients with shift from safety baseline to worst post-baseline values based on the confirmed results by toxicity grade for ALT, AST, and platelets will also be tabulated.

- Hemoglobin: shift from safety baseline to minimum post-baseline value
- WBCs: shift from safety baseline to minimum post-baseline value
- WBCs: shift from safety baseline to maximum post-baseline value
- Platelets: shift from safety baseline to minimum post-baseline value
- Creatinine: shift from safety baseline to maximum post-baseline value
- BUN: shift from safety baseline to maximum post-baseline value
- ALT: shift from safety baseline to maximum post-baseline value
- AST: shift from safety baseline to maximum post-baseline value

Hemoglobin change from baseline to minimum post-baseline value will be summarized by value category based on the toxicity grade as well.

Selected coagulation assessments shift from baseline to the worst post-baseline value will also be summarized by value category based on the toxicity grade.

- Activated Partial Thromboplastin Time: shift from safety baseline to maximum post-baseline value
- Prothrombin Time: shift from safety baseline to maximum post-baseline value
- Prothrombin Intl. Normalized Ratio: shift from safety baseline to maximum post-baseline value
- Fibrinogen: shift from safety baseline to minimum post-baseline value
- Fibrinogen: shift from safety baseline to maximum post-baseline value

LDL-C will be classified to ≥ 160 mg/dL (4.14 mmol/L) or < 160 mg/dL (4.14 mmol/L), and the incidence rate of shift from safety baseline to maximum post-baseline category will be summarized.

hsCRP will be classified to Normal or $>$ Upper limit of normal (ULN), and the incidence rate of shift from safety baseline to maximum post-baseline category will be summarized.

The incidence of patients with post-baseline platelet results falling in each of the following categories will be summarized for the safety set and the subset of patients with normal baseline ($\geq 140,000/\text{mm}^3$), and these categories will be summarized based on confirmed values as well:

- Any 2 occurrences of platelet count $< 140,000/\text{mm}^3$
- Any single occurrence of platelet count $< 100,000/\text{mm}^3$
- Any 2 occurrences of platelet count $< 140,000/\text{mm}^3$ or any single occurrence of platelet count $< 100,000/\text{mm}^3$
- Worst post-baseline value falling in: $100,000/\text{mm}^3$ to $< 140,000/\text{mm}^3$, $75,000$ to $< 100,000/\text{mm}^3$, $50,000$ to $< 75,000/\text{mm}^3$, $25,000$ to $< 50,000/\text{mm}^3$, 0 to $< 25,000/\text{mm}^3$
- Worst post-baseline platelet reduction from Baseline $\geq 30\%$ and $\geq 50\%$

The incidence of patients with post-baseline platelet results falling in each of the following categories will be summarized for the safety set and the subset of patients with normal baseline ($\geq 140,000/\text{mm}^3$):

- With ≥ 2 consecutive values of platelet count $< 140,000/\text{mm}^3$
- With platelet count $< 100,000/\text{mm}^3$ at final visit
- With ≥ 2 consecutive values of platelet count $< 140,000/\text{mm}^3$ or with platelet count $< 100,000/\text{mm}^3$ at final visit

The number of patients with any single occurrence of platelet results at any time, and during post-baseline period, falling in each of the following categories will be summarized for the safety set. These categories will be summarized based on nadir platelet values as well:

- $< 140,000/\text{mm}^3$
- $< 100,000/\text{mm}^3$
- $100,000/\text{mm}^3$ to $< 140,000/\text{mm}^3$
- $75,000$ to $< 100,000/\text{mm}^3$

- 50,000 to < 75,000/mm³
- 25,000 to < 50,000/mm³
- < 25,000/mm³

The ratio of post-baseline central lab platelet test numbers to total number of injections in open-label study will be summarized. The ratio of post-baseline central and local platelet tests numbers to total number of injections in open-label study will be also summarized.

The time to recover from confirmed platelet values <100,000/mm³ during on-study period will be calculated and summarized by all patients, and patients who complete week 52 (or week 104) with or without any dose pause/dose adjustment.

Summary figures will be generated for platelet counts over time (absolute values, absolute change from baseline, and percent change from baseline) in patients treated with placebo in ISIS 304801-CS6 who then treated with Volanesorsen in ISIS 304801-CS7.

A summary figure will be generated for platelet counts over time (mean and SEM of absolute values) for treatment naïve patients. The first event of platelet count < 50,000/mm³ will be annotated in the figure. This figure will also be generated by weight group (<70kg; >=70kg).

A scatter plot will be generated for nadir platelet counts during on-treatment period vs. selected factors:

Body Weight (kg)
BMI
The Total Number of Injections
Baseline Spleen Volume (mL)
Baseline Fasting Triglycerides (mmol/L)
Baseline Fasting Apolipoprotein CIII (g/L)

The incidence of patients with post-baseline lab results falling in each of the following categories will be summarized for the safety set:

- Any serum creatinine >=0.3 mg/dL higher than baseline
- Any serum creatinine >=50% higher than baseline
- Final visit serum creatinine >=0.3 mg/dL higher than baseline
- Final visit serum creatinine >=50% higher than baseline

Summary of selected hematology assessment (white blood cell count, neutrophil, hemoglobin, and hematocrit) over time will be generated. Summary of selected urinalysis assessment (urinary protein, and urinary albumin), and normalized urine albumin and protein to creatinine (urine albumin/creatinine ratio, urine protein/creatinine ratio) over time will be generated. Corresponding summary figures will be generated as well. Urine albumin/creatinine ratio will be calculated as 1000 * urine albumin (mg/dL) / urine creatinine (mg/dL),

Shift tables of on-study urine albumin/creatinine ratio and urine protein/creatinine ratio will be generated with below ranges:

Urine Albumin/creatinine ratio	Urine Protein/creatinine ratio
< 30 mg/g	< 150 mg/g
30 to < 300 mg/g	150 to < 500 mg/g
>= 300 mg/g	500 to < 1000 mg/g
	>= 1000 mg/g

A listing for patients with ALT or AST > 3 x ULN will be generated to present all ALT, AST, Bilirubin, and ALP records from central and local lab.

A listing will be provided for patients who terminated treatment due to a protocol-defined stopping rule (see Protocol section 8.6 for details) with categories (liver chemistry elevation, renal function test results, platelet count results) and narratives.

3.5.5 Exposure

Treatment duration in days, number of injections of Study Drug, compliance to Study Drug, dose adjustment and dose interruption/pauses will be summarized for the safety set.

- Treatment duration in days is defined as the last day on Study Drug minus the first day on Study Drug plus one. This will be derived for both index study period and the open-label study period.
- Number of injections of Study Drug received includes those for which full volume of dose was not given.
- Number of injections of Study Drug received for patients on active treatment in the index study will be the number of injections of Study Drug received from the first dose of the index study. Number of injections of Study Drug received for patients on placebo in the index study will be from the first dose of the open-label study.

Treatment duration in months during index study and open-label study will be summarized for the safety set.

- >=3 month category is defined as treatment duration in days >=85 days
- >=6 month category is defined as treatment duration in days >=176 days
- >=9 month category is defined as treatment duration in days >=267 days
- >=12 month category is defined as treatment duration in days >=358 days
- >=18 month category is defined as treatment duration in days >=541 days
- >=24 month category is defined as treatment duration in days >=723 days

Compliance to Study Drug will be summarized by descriptive statistics.

- Compliance of the open-label study for Group 1, Group 2 and Group 3 will be calculated as follows:
$$100 \times (\text{number of injections of Study Drug in the open-label study}) / (\text{number of injections scheduled during the Open-label Study Treatment Period})$$

- Compliance of the index study (ISIS 304801-CS6 or ISIS 304801-CS16) and open-label study overall for Group 1 and Group 2 will be calculated as follows:

$$\frac{100 \times (\text{number of injections of Study Drug in the index study (ISIS 304801-CS6 or ISIS 304801-CS16)} + \text{number of injections of Study Drug in the open-label study})}{(\text{number of injections scheduled during the treatment period in the index study (ISIS 304801-CS6 or ISIS 304801-CS16)} + \text{number of injections scheduled during the treatment period in the open-label study})}$$

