Any patient who discontinues early from the Treatment Period should be followed as per the platelet monitoring rules shown in Section 8.6.3 of the protocol for the first 6 weeks after discontinuing Study Drug. Following this period, if the platelet count is stable (at least 3 consecutive values that are stable as determined by the Sponsor Medical Monitor and $> 100,000/\text{mm}^3$), the next platelet count should be taken within at least 6 weeks so that patients are monitored for at least 12 weeks after discontinuing Study Drug. Patients should also be strongly encouraged to attend applicable landmark visits at Weeks 12, 13, 25, 26, and 50, 52 (calculated based on the time elapsed since Day 1) to collect fasting lipid panels and conduct safety assessments in accordance with the Schedule of Procedures. Any patient who discontinues treatment after Week 44 should also be strongly encouraged to attend a final follow-up visit (Week 65 visit assessments) approximately 13 weeks after their last dose of Study Drug, in addition to the applicable landmark visits.

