2.1.3 Extended Treatment Period

Patients will have the option of continuing treatment for up to an additional 52 weeks until an expanded access program is approved and available in their country.

During the extended treatment period, patients will report to the study center for clinic visits during Weeks 54-104 (see Schedule of Procedures in Appendix A of the protocol). Study Drug will be administered once weekly unless the patient is on a biweekly treatment schedule for safety reasons. Collection and measurement of vital signs, clinical laboratory parameters (including hematology, serum chemistry, and urinalysis), AEs, concomitant medication/procedure information, lipid panel, volanesorsen plasma concentrations, IM testing, ECGs, and physical examinations will be performed according to the Schedule of Procedures in Appendix A. Adverse events at the injection site should

be collected as adverse events. Dietary counseling will be reinforced at intervals throughout the extended treatment period. All blood and urine samples should be collected prior to volanesorsen administration. Blood sampling at Weeks 53, 54, 55, 56, 57, 58, 59, 60, 61, 62, 63, 65, 66, 67, 68, 69, 70, 71, 72, 73, 74, 75, 77, 78, 79, 80, 81, 82, 83, 84, 85, 86, 87, 88, 89, 91, 92, 93, 94, 95, 96, 97, 98, 99, 100, 101, 102, and 103 may be conducted by a home healthcare nurse. Approval for study procedures to be conducted by a home healthcare nurse on other outpatient visit days will require prior approval by the Sponsor. Patients must be fasted prior to drawing all blood samples and samples drawn locally should also be sent to the central laboratory for analysis whenever possible. Treatment instructions and training will be provided to the patient where applicable.

2.1.4 *Pharmacokinetic (PK) Subgroup*

A subgroup of patients will participate in an extended PK collection. Patients in this subgroup will have more frequent PK sampling over a 24-hour period following the first dose on Study Day 1 in order to evaluate the plasma PK parameters of volanesorsen. Patients in this subgroup will have an additional visit to the clinic, or by a home healthcare nurse, on Day 2 to collect a 24-hour post-dose blood draw after dosing on Day 1. The detailed PK sampling schedules are outlined in Appendix C of the protocol.

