Participation in the PK subgroup is optional for sites and patients, and consent may be withdrawn for the subgroup-specific procedures (e.g., multiple blood draws for PK) without being withdrawn from the study. If a patient withdraws consent from the subgroup procedures, he/she should remain on study and continue to follow all the non-subgroup assessments and procedures as outlined in Appendix A of the protocol.

2.1.5 *Post-Treatment Period*

After completion of the Week 52 visit assessments, patients will have the option of participating in an expanded access program or continuing dosing for up to an additional 52 weeks until an expanded access program is approved and available in their country. Patients not participating in an expanded access program will enter the 13-week post-treatment evaluation period. This 13-week post-treatment evaluation period consists of 4 Study Center visits on Weeks 54, 56, and 58 (which may be conducted by a home healthcare nurse), and Week 65 as outlined in the Schedule of Procedures in Appendix A of the protocol. Patients who complete, or terminate early from, the extended treatment period without subsequently participating in an expanded access program will enter a 13-week post-treatment evaluation period consisting of 4 Study Center visits on Weeks 106, 108, and 110 (which may be conducted by a home healthcare nurse), and Week 117 as outlined in the Schedule of Procedures in Appendix A of the protocol.

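### Are the >=18 and >=24 month exposure cut-offs (541 and 723 days) one day too late?

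*SAP*

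**What the plan says.** Section 3.5.5 (Exposure) gives the measure: "Treatment duration in days is defined as the last day on Study Drug minus the first day on Study Drug plus one". It then lists six cumulative categories, with lower limits of 85, 176, 267, 358, 541 and 723 days for 3, 6, 9, 12, 18 and 24 months. The last three read ">=12 month category is defined as treatment duration in days >=358 days", ">=18 month category is defined as treatment duration in days >=541 days" and ">=24 month category is defined as treatment duration in days >=723 days". No derivation is given.

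The study calendar is set elsewhere. The visit-window table in Section 3.2.1 puts Week 52 at Day 358, Week 78 (a France-only quality-of-life visit) at Day 540 and Week 104 at Day 722. The PK schedules in Section 3.4.1.1 take pre-dose samples on Days 358 and 722, each with a window of 2 days either way. The table in Section 3.3 ends its 15–18 month period at day 546 (Week 78) and its 21–24 month period at day 728 (Week 104). Under Section 2.1.3, dosing after Week 52 may continue for "up to an additional 52 weeks until an expanded access program is approved".

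**The concern.** The first four limits are exactly the days on which the Week 13, 26, 39 and 52 doses fall due, so it is natural to read the list as a list of dosing days. On that reading the last two should be 540 and 722.

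The SAP also treats Weeks 52 and 104 as matching end points. Section 3.5.4.2 groups "patients who complete week 52 (or week 104) with or without any dose pause/dose adjustment", and in Section 2.1.5 the follow-up after extended treatment is described as "consisting of 4 Study Center visits on Weeks 106, 108, and 110 (which may be conducted by a home healthcare nurse), and Week 117", which mirrors the Week 65 visit after the first 52 weeks. A patient who finishes the first period on the scheduled day enters the 12-month row, but one who finishes the extended period on the scheduled day misses the 24-month row.

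In an extension study of up to about 70 patients, meant to describe extended dosing, the number treated for 24 months is a figure readers will look at. An off-by-one limit that dropped on-schedule completers would understate it.

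**Working it through.** **Inputs.** Target day of Week n is (n − 1) × 7 + 1 (Section 3.2.1). Duration is last day minus first day plus one (Section 3.5.5), so with a first dose on Day 1 it equals the study day of the last dose.

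**The two candidate rules against the SAP's limits.** The week rule is (n − 1) × 7 + 1. The calendar rule rounds months × 365/12 up to a whole day and subtracts 7, that is, one weekly dosing interval.

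| Months | Week | SAP limit | Week rule | months × 365/12 | Rounded up, − 7 |
|---|---|---|---|---|---|
| 3 | 13 | 85 | 85 | 91.25 | 92 − 7 = 85 |
| 6 | 26 | 176 | 176 | 182.5 | 183 − 7 = 176 |
| 9 | 39 | 267 | 267 | 273.75 | 274 − 7 = 267 |
| 12 | 52 | 358 | 358 | 365 | 365 − 7 = 358 |
| 18 | 78 | 541 | 540 | 547.5 | 548 − 7 = 541 |
| 24 | 104 | 723 | 722 | 730 | 730 − 7 = 723 |

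The week rule gives four of the six; the calendar rule gives all six. The pattern also shows directly: 176 + 365 = 541 and 358 + 365 = 723, so the 18- and 24-month limits are the 6- and 12-month limits plus one calendar year. Fifty-two weeks are only 364 days, which is where the one-day difference arises.

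**Agreement with Section 3.3.** The Week 78 dosing week covers days 540–546 and the Week 104 week covers days 722–728. Both 541 and 723 lie inside them, and so inside the periods ending at days 546 and 728. Nothing there is contradicted.

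**Who would change row with 722 in place of 723.** Take last doses across the 2-day PK visit window at Week 104:

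| Last dose on Day | >=723 | >=722 |
|---|---|---|
| 720 | no | no |
| 721 | no | no |
| 722 | no | yes |
| 723 | yes | yes |
| 724 | yes | yes |

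Only Day 722 moves. The 12-month row behaves the same way: last doses on Days 356 and 357 are inside the Week 52 window and miss 358. Neither row counts completers, and neither limit would make it do so. Completion of treatment is reported separately under disposition (Section 3.2.4).

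**The 18-month limit.** Week 78 ends no treatment period. Only a patient who happens to stop on exactly Day 540 would move.

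**Patients treated in an index study.** Assume 52 weekly doses in CS6 (358 days) and 26 in CS16 (176 days), and add the periods:

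- CS6 plus 52 weeks: 358 + 358 = 716
- CS16 plus 52 weeks: 176 + 358 = 534
- CS6 plus 104 weeks: 358 + 722 = 1080
- CS16 plus 104 weeks: 176 + 722 = 898

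None of these totals changes category between 541/723 and 540/722.

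**The case for a change.** The strongest case for a defect is that the calendar rule is a reconstruction. The SAP does not state it, and it needs a 365-day year, whereas Section 3.2.1 uses 365.25 for patient-years. With 365.25 the same rule, rounded up, gives 359 at 12 months (358.25) and 724 at 24 months (723.5), which do not match. The week calendar, by contrast, is printed in the SAP, and Section 3.3 maps months to 13-week blocks. Whatever the source of 723, a patient stopping on Day 722 is left out and one stopping on Day 358 is counted.

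The day counts in that argument are right, and so is the point that the SAP leaves the conversion unexplained. But the week rule is not stated for this table either; it is inferred from four values and fails on the other two. A rule that the SAP does not adopt cannot be used to show that the SAP miscalculated.

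Two supports are weaker than they look. The Week 65 visit is described as a "final follow-up visit (Week 65 visit assessments) approximately 13 weeks after their last dose of Study Drug", but that sentence in Section 2.1.2 concerns patients who stop early after Week 44 and does not fix Day 358 as the scheduled last dose; the PK schedule is the better evidence. And the exclusion depends on reading the last day on drug as the last dose date. The match at 358 favours that reading, but if exposure ran to the end of the last weekly interval, the Week 104 patient would have 722 + 6 = 728 days and be counted.

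One uncertainty remains. The SAP does not say how index and open-label durations are combined for this table. If they were taken as one span from first to last dose, a CS6 volanesorsen patient with exactly 7 days between the last index dose and open-label Day 1 would reach 358 + 6 + 358 = 722 at Week 52 and would also sit on the boundary. That could add to the patients affected, but it does not make 723 wrong.

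**Conclusion.** The concern does not hold. The limits of 541 and 723 days break no stated rule or calculation, agree with the month periods in Section 3.3, and fit one coherent calendar rule together with the other four. Both 722 and 723 are short of 24 calendar months (730 days), so choosing between them is a labelling convention.

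On open-label duration, the difference affects only a last dose on exactly Day 540 or Day 722. The SAP does not give the number of such patients, and it may be zero, since patients can leave for expanded access before Week 104. It touches one descriptive table in a study without a formal hypothesis; duration in days, patient-years and the conclusions are the same under either limit.

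This rests on reading the last day on drug as the last dose date and on weekly dosing. For index-study patients it also rests on adding the two periods, with the assumed 52 and 26 weekly doses. A sentence giving the month-to-day conversion would help a reader, but its absence is not an error.
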